### **Informed Consent, Screening and Baseline**

Participants will be pre-screened over the phone to determine whether basic inclusion criteria are met. If the participant passes the phone screen, an in-person assessment/baseline visit will be scheduled.

At the in-person screening/baseline visit, informed consent with HIPAA authorization will be obtained prior to initiation of study procedures.

### **Screening.**

The following measures will be used to determine eligibility criteria, and to gather baseline characteristics of the sample

Demographics Questionnaire – A demographics questionnaire will collect demographic information including age, race, education, military history, and history of justice-involvement.

The Traumatic Life Events Questionnaire [TLEQ; (E.S. Kubany et al., 2000)] is a brief self-report inventory that asks about exposure to 21 kinds of potentially traumatic events from natural disasters to sexual abuse. The TLEQ provides a 7-point response format to indicate frequency of occurrence. This instrument allows for detailed assessment of trauma exposure prior to military service, during military service, and following military service. TLEQ results in trauma exposure summary categories of combat, childhood sexual assault, childhood violence, adult sexual assault, attack, illness and accident. This measure will be administered at baseline to provide an index of the range of trauma exposure in the sample.

The Clinician-Administered PTSD Scale (CAPS) (F. W. Weathers et al., 2013) will be administered to evaluate for current PTSD at baseline and at follow-up. To minimize bias in outcomes evaluation, the clinician who conducts the therapy may administer the baseline CAPS, but will not administer the follow-up CAPS. The CAPS has been extensively used with Veterans, and its strong evidence of reliability and validity have established it as the “gold standard” for PTSD assessment. PTSD symptoms will be considered present based on the CAPS frequency  $\geq 1$ /intensity  $\geq 2$  rule (Weathers, Keane, & Davidson, 2001). For Veterans with multiple traumas, CAPS administration will be modified as recommended by the authors of Narrative Exposure Therapy (Schauer et al., 2011). Specifically, rather than requiring Veterans to choose from among multiple events which is the most traumatizing, we will ask Veterans to identify a “type” of

trauma (sexual assaults), or a life period during which they experienced multiple traumas (i.e. combat deployment), upon which to evaluate their experience of PTSD symptomatology.

*The Structured Clinical Interview for DSM-V Disorders Research Version* (SCID; (First, Williams, Karg, & Spitzer, 2015)) (selected modules) will be administered to assess for active psychosis and severe substance abuse.

Diagnostic raters will be trained using SCID and CAPS standardized training, which includes review of interview manuals, training videotapes, and co-rating training with an experienced rater. Interrater reliability based on videotapes of patient interviews for Axis I diagnoses across previous studies has been excellent (kappa = .96).

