### **Post-treatment Follow-up Visits**

In-person follow-up interviews and assessments will be conducted with each Veteran participant. Follow-up will occur 1 to 2 weeks after the final therapy session (for completers) or 11 to 12 weeks after baseline (for those who drop out) to assess changes in PTSD, perceptions of moral injury, anger, aggression, trauma-related guilt, depression, substance use, and suicide-related constructs. For those randomized to TAU, follow-up will occur 11 to 12 weeks after

baseline. The CAPS and all baseline assessments will be re-administered. The CAPS will not be administered by any of the study therapists. To assess the degree to which participants trusted and felt respected and understood by the therapist, the *Helping Alliance Questionnaire* (Luborsky *et al.*, 1996) will also be administered at the follow-up visit.

Qualitative interviews following an interview guide will be administered to all participants. For those completed treatment, questions will evaluate treatment acceptability, as well as participants' impressions of whether and how the therapy was (or was not) helpful to them. For those who dropped out, reasons for dropout at each treatment phase will be explored. The qualitative portion of the post-treatment follow-up visit will be audio recorded using the Olympus DM-720 4GB Digital Voice Recorder or the Olympus DM-620, which are newer models of the approved-for-use Olympus DM-420. Recordings will be transcribed and analyzed using thematic analysis.

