### **Three-month Follow-up**

Three months after the final treatment session, packets of questionnaires including the baseline measures will be mailed along with a self-addressed, stamped return envelope, to participants regardless of drop-out status.

Measure	Screening	Baseline	Post-treatment	3 months
Demographics Questionnaire	X			
The Traumatic Life Events Questionnaire	X			
The Clinician-Administered PTSD Scale	X		X	
The Structured Clinical Interview for DSM-V (Psychosis, Substance Misuse Modules)	X			
The Appetitive Aggression Scale		X	X	
The Killing Cognitions Scale*		X	X	
PTSD Checklist for the DSM-5 (PCL-5)**		X	X	X
The Moral Injury Events Scale		X	X	X
Revised Conflict Tactics Scales		X	X	X
Dimensions of Anger Reactions		X	X	X
Trauma-Related Guilt Index		X	X	X
Beck Depression Inventory		X	X	X

Acquired Capability for Suicide Scale - Fearlessness About Death		X	X	X
Depressive Symptom Index: Suicidality Subscale		X	X	X
Interpersonal Needs Questionnaire		X	X	X
The Alcohol Use Disorder Identification Test		X	X	X
The Drug Abuse Screening Test		X	X	X
The Helping Alliance Questionnaire			X	

\* The Killing Cognitions Scale will only be administered if participants endorse having killed in the context of war on Part 1 of the Appetitive Aggression Scale.

\*\* To evaluate the change in PTSD symptoms over time, participants will be administered the PCL-5 at each session.

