To evaluate participant retention through the 3 month assessment, we will consider the larger RCT feasible if 70% of Veterans complete the 3 month assessment. As recommended by Wisniewski and colleagues (Wisniewski, Leon, Otto, & Trivedi, 2006), we will maintain frequent participant contact throughout the evaluation period. For example, we will make intermittent phone calls to participants to check on their status, and send birthday and holiday cards to encourage a sense of community and ownership of the study.

Adverse event monitoring is discussed in detail in the Human Subjects section of this proposal. Though we do not anticipate adverse events to be frequent or severe, if we observe a problem with adverse events we will build precautions into the structure of the treatment protocol and the study design.

***Specific Aim 2. Collect data on appropriateness of assessment measures for measuring key clinical constructs in Veterans with a history of aggression. Clinical outcomes evaluated will include PTSD symptoms, suicidality, substance abuse, and aggression.***

Change scores from baseline to 3 months post-baseline on the CAPS and on measures of PTSD symptom severity, perceptions of moral injury, anger, aggression, trauma-related guilt, depression, substance use, and suicide-related constructs will be calculated using the measures listed in the baseline section above. Measures will be evaluated for acceptable variability, and for absence of floor or ceiling effects in this sample.

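### Does letting the treating clinician rate the baseline CAPS, but not the follow-up CAPS, bias the CAPS change score?

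*Protocol*

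**What the plan says.** Screening sets the baseline rule: "the clinician who conducts the therapy may administer the baseline CAPS, but will not administer the follow-up CAPS". This is a permission, not a requirement. Post-treatment Follow-up Visits sets the rule for the other end: "The CAPS will not be administered by any of the study therapists".

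In the schedule table under Three-month Follow-up, the row for "The Clinician-Administered PTSD Scale" is marked at screening and post-treatment only. The baseline CAPS also serves eligibility, since Screening introduces its instruments with "The following measures will be used to determine eligibility criteria".

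On rater quality, Screening says "Diagnostic raters will be trained using SCID and CAPS standardized training", with co-rating alongside an experienced rater, and reports a kappa of .96 for Axis I diagnoses in previous studies.

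For Specific Aim 2, Evaluation of Specific Aims calculates "Change scores from baseline to 3 months post-baseline on the CAPS" and on the other clinical measures. It then says what will be done with them: "Measures will be evaluated for acceptable variability, and for absence of floor or ceiling effects in this sample".

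**The concern.** A change score depends on both of its ends. If therapists rate some baselines and never rate a follow-up, the class of rater changes once, always in the same direction. With only two CAPS occasions, no third rating is available to separate a rater effect from change over time. If therapists score severity higher than independent raters, part of the apparent improvement is an artefact; if they score lower, improvement is understated.

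The reported kappa does not settle this, because it describes agreement on diagnoses rather than on CAPS severity. The Specific Aims section also says that the team wants to know whether the therapy might affect key clinical outcomes, PTSD symptoms among them. One sentence in Overview of Study Visits has all eligible Veterans assigned to NET. If that were the design, within-group change would be the only clinician-rated signal of such an effect.

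**Working it through.** **Inputs from the protocol.** Participants gives 20 enrolled from 29 baseline assessments at 70% eligibility. The figure reproduces: 20 / 0.70 = 28.57, rounded up to 29. The therapist share at follow-up is 0 by rule. The therapist share at baseline (p) and the mean therapist-minus-independent difference (d) are not given.

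**The identity.** Mean observed baseline = true mean + p × d. Mean observed follow-up = true mean, because no therapist rates it. So follow-up minus baseline = true change - p × d. A simulation returned shifts of -0.50, -1.00, -2.00 and -5.00 for p × d of 0.5, 1, 2 and 5. Because the same CAPS decides entry, the identity is slightly altered by selection. With an assumed true baseline of mean 35 and SD 10, rater error SD 4 and an entry cut at 25, the shift at p = 1 was -1.90 for d = 2 and -4.78 for d = 5.

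**Size on assumed values.** Take d of 1, 2 or 5 points in either direction and an SD of change of 8 to 14, all assumptions. With 20 participants in one group, the SE of mean change is 8 / √20 = 1.79 to 14 / √20 = 3.13. The table gives the absolute shift in points, with multiples of the SE in brackets.

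| p | d = 1 | d = 2 | d = 5 |
|---|---|---|---|
| 0.25 | 0.25 (0.08–0.14) | 0.5 (0.16–0.28) | 1.25 (0.40–0.70) |
| 0.5 | 0.5 (0.16–0.28) | 1.0 (0.32–0.56) | 2.5 (0.80–1.40) |
| 1 | 1.0 (0.32–0.56) | 2.0 (0.64–1.12) | 5.0 (1.60–2.80) |

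Six of the nine cells stay below one SE across the whole SD range. Only p = 1 with d = 5 exceeds one SE throughout. If p or d is zero, so is the shift.

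**Between arms.** With a control arm the residual is -(p_NET - p_TAU) × d. The CAPS helps to decide eligibility, which implies that it precedes allocation; p then has the same expectation in both arms and the residual is 0 in expectation. A chance split of 0.6 versus 0.4 would leave -0.4 points at d = 2 and -1.0 at d = 5.

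**What the protocol does with the result.** Each stated use was checked against the shift.

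- Retention must exceed 80%, counted in sessions attended. No CAPS score enters.
- The larger trial is feasible if 70% complete the 3-month assessment, which is a mailed packet without the CAPS.
- Recruitment is tracked as the number completing the in-person screening, which does not depend on who rates.
- Variability: mixing two rater classes adds p(1 - p)d² to the baseline variance. At p = 0.5 and d = 5 that is 0.25 × 25 = 6.25. On an assumed baseline SD of 10, the SD becomes √106.25 = 10.31, about 3% more. At p = 1 nothing is added.
- Floor or ceiling effects: a shift of a few points matters only if scores already crowd one end of the scale.

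**What a stricter rule would take.** Barring therapists at baseline moves p × 29 interviews to the non-therapist raters: 7.25, 14.5 or 29 at p = 0.25, 0.5 or 1. Against at most 20 follow-up interviews, that is 36%, 73% or 145% more work for a group whose number the protocol does not give.

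**The case for a change.** The best case for the concern is that the protocol justifies its rater rule as protection against bias in outcome evaluation, and a rule that covers one end of a change score protects only partly. Who rates is a matter of conduct, so no later analysis can repair it. Comparing participants by baseline rater role is possible when p lies between 0 and 1, but role is not randomly assigned. Even at 10 versus 10, with SDs of 10 to 15, the SE of the difference is 10 × √(1/10 + 1/10) = 4.47 to 15 × √(1/10 + 1/10) = 6.71 points. Non-therapist raters already exist, so the stricter rule needs no new role.

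Part of this stands. The mechanism is real, the kappa does not exclude it, and a common rater pool would be tidier. Three points keep it from being a fault.

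- At screening no therapy has been given, so the therapist has no result of their own to rate. The strong incentive arises at follow-up, where the bar is complete. Shared CAPS training with co-rating also bears on d.
- The harm depends mainly on the sentence assigning every eligible Veteran to NET. The same section calls the design randomized and controlled, Study Visits and Post-treatment Follow-up Visits describe TAU participants, and Participant Payment mentions two arms. That inconsistency is a separate matter and cannot supply the consequence here.
- The interest in a possible effect on PTSD symptoms is also served by the self-report PCL-5, given at baseline, every session, post-treatment and 3 months, which does not depend on the CAPS rater.

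**Conclusion.** The concern does not hold. The rules at baseline and follow-up fit together, and the stricter one is placed where the risk of biased rating is greatest. The possible shift in mean CAPS change is -p × d, but the protocol gives neither quantity, either may be zero, and the sign of d is open, so a bias is conceivable but not shown. On the assumed values it ranges from 0.25 to 5 points, and it reaches the upper end only if every baseline is therapist-rated and the raters differ by 5 points.

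No threshold or stated use of the data turns on mean CAPS change. Under the randomized design the term vanishes between arms in expectation, provided the baseline CAPS precedes allocation, as its role in eligibility implies. A stricter baseline rule costs little only where p is near 0, and there it gains almost nothing; where it could help, it adds up to 29 interviews. That is a staffing trade-off on which reasonable teams may differ, and the protocol need not change on this point. The conclusion rests on the CAPS keeping its descriptive role: a single-arm efficacy claim based on CAPS change would reopen the question.

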### **Baseline measures.**

If a Veteran is determined to meet inclusion criteria and agrees to participate in the study, the following baseline assessments will be administered. These assessments will also be administered at post-treatment and both mailed follow-ups, unless otherwise indicated.

*The Appetitive Aggression Scale (AAS) (Weierstall & Elbert, 2011)*. This scale has two parts. Part 1 is a 17-item scale that asked participants to mark whether they have engaged in or witness specific violent acts. Fifteen of these items measure acts that could reflect appetitive aggression (e.g. "...made another person scream in pain"), and two are more clearly reactive (e.g. "...defended yourself in a fight"). If a participant endorses having engaged in any of the 15 potentially appetitive aggressive behaviors, then Part 2 will be administered. Part 2 is a 19-item scale that asks participants to rate their perceptions of aggression on a 5-point Likert scale ranging from 0 (disagree) to 4 (agree). Part 2 of the scale has been demonstrated to have acceptable reliability, and has been shown to measure a construct distinct from other conceptualizations of aggression (Weierstall & Elbert, 2011). This scale will only be administered at baseline and post-treatment.

### *Killing Cognitions Scale (KCS) (Maguen et al., 2017)*

The KCS includes 55 items that evaluate several constructs identified as associated with distress in Veterans who have killed in the context of war. It is currently under psychometric evaluation by the authors; we have obtained permission to use it for this study from the primary author, [name]. This scale will only be used with participants who endorse having killed in the context of war on Part 1 of the Appetitive Aggression Scale (AAS).

*PTSD Checklist for the DSM-5 (PCL-5) (Weathers et al., 2013)*. On the PCL-5, participants first report an autobiographical narrative of a trauma, and subsequently rate how bothered they were by each symptom (0 [not at all] – 4 [extremely]) for all DSM-V PTSD symptoms within the past week. Psychometric testing is currently underway on the newest version of the PCL; previous versions have been found to have high reliability and validity across trauma populations.

*The Moral Injury Events Scale (MIES) (Nash et al., 2013)*. The MIES is an 11-item scale that measures moral injury associated with experiences during military service. Statements related to distress or feelings of betrayal related to potentially morally injurious events are rated on a 6

point scale ranging from 1 (strongly agree) to 6 (strongly disagree). Three factors have been identified: Transgressions-Self, Transgressions-Other, and Betrayal. In two samples of Army and Air Force personnel, Cronbach's alphas for the three scales ranged from .79 to .96, and results provided evidence of construct validity as well (Bryan et al., 2016).

*Revised Conflict Tactics Scales (CTS2) (Straus, Hamby, Boney-McCoy, & Sugarman, 1996)*. The CTS2 includes 78 items measuring the use of psychological and physical attacks by the participant, as well as the experience of such attacks. Participants answer how often these behaviors were perpetrated against them within a specified time period, as well as how often they have perpetrated these aggressive behaviors over that same period: 0 (never); 1 (once); 2 (twice); 3 (3-5 times); 4 (6-10 times); 5 (11-20 times); 6 (more than 20 times). The original CTS2 indexed a time period of one year, and was specific to aggression with an intimate partner. Consistent with previous studies on Veterans and violence (Beckham et al., 1997), the original CTS2 instructions will be modified in 2 ways to more appropriately reflect the goals of this study: 1) the target of the behavior will be expanded from "partner" to "anyone"; and 2) the time frame of the response will be reduced from one year to three months to detect potential changes associated with treatment. The CTS2 includes the following subscales: Negotiation, Psychological Aggression, Physical Assault, Sexual Coercion, and Injury. Coefficient alphas for the CTS2 subscales range from .07 to .95, with good evidence of construct validity (Straus et al., 1996).

*Dimensions of Anger Reactions (DAR) (Novaco, Swanson, Gonzalez, Gahm, & Reger, 2012)*. The DAR is a 7-item scale measuring the frequency, duration, and behavioral response to anger, and anger-related functional impairment on social relationships, health, and work. It was found to have concurrent and discriminant validity, and to correlate highly with measures of functional impairment, in a large sample of treatment-seeking soldiers who had served in Iraq or Afghanistan. The DAR will be administered at baseline, at each study visit, and at follow-up to provide information about the pattern of change in anger- and aggression-related cognitions over the course of the intervention.

*Trauma-Related Guilt Index (TRGI) (Edward S. Kubany et al., 1996)*. Guided by appraisal theories of emotion, the 32-item TRGI is an index of guilt associated with the experience of trauma. Participants rate statements on a 5-point scale ranging from extremely true/extremely guilty (4) to not at all true/not guilty at all (0). Factor analyses has revealed four scales: Hindsight-Bias/Responsibility, Distress, Violation of Personal Standards, and Lack of Justification. Evidence of internal consistency and validity has been found in several samples.

*Beck Depression Inventory (BDI-2) (Beck, Steer, & Brown, 1996)*. The BDI-2 is a 21-item scale that evaluates symptoms of depression. It is widely used both clinically and in research, and has been found to have high internal consistency (coefficient alpha = .91) with good evidence of convergent validity (Dozois, Dobson, & Ahnberg, 1998).

*Acquired Capability for Suicide Scale - Fearlessness About Death (ACSS-FAD) (Ribeiro et al., 2014)*. The Interpersonal Theory of Suicide holds that the capacity to commit suicide requires a sense of fearlessness about death and an elevated pain tolerance, both of which can develop as a

result of repeated exposure to horrifying experiences involving pain or death. Such experiences are not uncommon in soldiers, theoretically increasing their risk for suicidal behavior. The ACSS-FAD is a 7-item scale that evaluates fearlessness about death. Participants rate each item on a scale of 0 (not at all like me) to 4 (very much like me). The scale has been found to have good reliability and validity (Ribeiro et al., 2014).

*Depressive Symptom Index: Suicidality Subscale (DSI-SS) (Joiner, Pfaff, & Acres, 2002)*. The 4-item scale screens for suicidal ideation over the prior two weeks. Participants rate each item on a scale of 0 (e.g. "I do not have thoughts of killing myself") to 3 (e.g. "I always have thoughts of killing myself"). Strong evidence of reliability and validity has been observed for this scale (Joiner et al., 2002).

*Interpersonal Needs Questionnaire (INQ) (Van Orden, Cukrowicz, Witte, & Joiner Jr, 2012)*. Based upon the Interpersonal Theory of Suicide (Joiner Jr et al., 2009), the INQ measures two proximal causes of the desire for suicide: Thwarted belongingness and perceived burdensomeness. Participants rate each of the 15 items on a scale of 1 (not at all true for me) to 7 (very true for me). Support for the reliability and validity of these scales has been observed across ages and in samples with varying degrees of psychopathology (Van Orden et al., 2012).

*The Alcohol Use Disorder Identification Test (AUDIT) (Bradley, Bush, McDonell, Malone, & Fihn, 1998)* contains 10 multiple choice questions about behavior and symptoms related to alcohol consumption. *The Drug Abuse Screening Test (DAST) (Skinner, 1982)* contains 20 "yes/no" questions about behavior and symptoms pertaining to substance use. Both the AUDIT and the DAST have shown excellent psychometric properties in studies of Veterans.

## Study Visits

Three licensed clinical psychologists who have been trained by some of the original developers in Narrative Exposure Therapy will provide therapy in this study. As needed, consultation will be provided via telephone or video conferencing by national expert on NET, [name]., and/or by one of the developers of FORNET, [name].

Participants will attend 10 weekly study visits of 90 minutes each. Session one will involve a psychoeducation session wherein the symptoms and etiology of PTSD are explained, and the rationale for treatment is provided. Session two will include development of the lifeline, during which the participant provides an overview of their life using a rope or string as symbol of the passage of time. The participant places flowers along the rope to symbolize positive events or relationships, and stones to symbolize negative events or traumas. A key element of VETNET is that the therapist will elicit discussion of what are often life-altering military-related events including military training, deployments, and separation from the military.

While creating the lifeline, participants will be offered the option to use sticks to symbolize events where they harmed another person. If participants do not indicate that they have ever harmed another person, then the adapted NET protocol will be used, though the possibility of using FORNET adaptations will be kept open if disclosure of harm is made later on in therapy. If participants do choose to use sticks in their lifeline, then the therapist will be alert to the possibility of needing to address moral injury or appetitive aggression by using adaptations specific to the FORNET protocol. In sessions three through nine participants will narrate key

events in their lives, with specific focus on traumatic events as well as events when they harmed another person. During traumatic event narration, therapists will guide participants through slowly explaining the details of the event to allow for exposure and processing of previously avoided emotions, sensations, and thoughts. Therapists will encourage participants to stay in the trauma memory until anxiety, or other strong emotion, has peaked and has begun to subside. During narration of perpetration events, therapists will use a similar protocol, and will focus on contextualizing the perpetration event and contrasting the memory feelings (what was experienced at the time of the event) with the participant's feelings in the here and now while recalling the event. After each session, the therapist will create the written version of the narrative, and this will be read to the participant at the beginning of the following session. After the participant has made corrections or additions to the narrative, the process will proceed to the next critical event.

For all Veterans, whether the NET or FORNET protocol is used, therapists will include in the final session a component that will be unique to VETNET and that draws upon elements of Acceptance and Commitment Therapy (Hayes, 2004) and Adaptive Disclosure Therapy (Litz et al, 2009). This session will include an invitation to Veterans to consider how they will reconnect with their communities in ways that will build upon their strengths. The therapist will work with Veterans to identify their values, and how they would best act upon these to contribute in meaningful ways to their communities. Examples could be working at an animal shelter, volunteering at a church, joining a Veterans' service organization, or volunteering for a community garden, homeless shelter, or Habitat for Humanity. The therapist will help Veterans identify clear behavioral goals for following through on these ideas. The end of the final session will also include an evaluation and referral to services the Veteran is eligible for either within the VA or in the community such as housing assistance, educational assistance, or employment training, to continue to support successful reintegration.

In the final session, the lifeline will also be recreated. The participant will be invited to reflect on the meaning that they attribute to the events, and to develop perspectives for the future. The final session also includes asking the patient to recall a recent prosocial event where they experienced feelings of excitement, power, enjoyment, pride, or control, and to recount this in detail. Rather than continuing the story until the intensity of the emotion diminishes, however, the therapist will stop the narration at the most exciting part. This experience is intended to prime the creation of a positive associative network with prosocial experiences, and to reinforce the sense that the patient can create positive experiences in the future that are aligned with an identity consistent with their values.

To evaluate the change in PTSD symptoms over time, participants will be administered the PCL-5 and DAR at each session.

Participants randomized to TAU will be contacted by phone once each week by the study coordinator for a brief check-in and to complete a PCL-5 and DAR.

